5. PROTECTION OF HUMAN SUBJECTS

5A. Risks to Subjects

5A.1. Human Subjects Involvement, Characteristics, and Design. The proposed research involving human subjects will be conducted by Klein Buendel, Inc. (KB: FWA No. 00003715).

The subject population for this study will be teens with Sickle cell disease (SCD) and their parent. Participants will consist of both males and females and participants will be of African American, Hispanic, and white race/ethnicity. All participants will be asked to complete a demographics form. The demographics are detailed in Section 7 and the Targeted Enrollment Table.

Human Subjects will include:

1. Usability Testing Participants (n = 14) will evaluate the user interface, ease of use, and perceived barriers in order to optimize the app prior to large scale evaluation. The purpose of usability

testing is to validate the app's design and to identify and correct problems prior to the evaluation period. A parent will give consent; teens will give assent. Consent and assent forms and procedures will be IRB-approved. Eligibility criteria are: a) age 13-17 years; b) diagnosed with SCD; c) own a smartphone or tablet, and d) read and speak English. Compensation will be \$25.

2. Evaluation Period Participants (n=100) will test the full *Pinpoint* app using a within-subjects pre-post design over 12 weeks to evaluate changes in (1) knowledge acquisition for communicating about pain and types of SCD pain; (2) the Pain Assessment Tool; (3) SCD general knowledge and self-efficacy; (4) family cohesion; and (5) app usage. A parent will give consent; teens will give assent. Consent and assent forms and procedures will be IRB-approved. Eligibility criteria are: a) age 13-17 years; b) diagnosed with SCD; c) own a smartphone or tablet, and d) read and speak English. Participants will use the app for 12 weeks after a one-on-one orientation to the app where teens will be assisted with app download, provided instructions on how to use the app, and encouraged to use the app daily. Participants will complete a baseline, a 6-week, and a 12-week assessment. Participants will be compensated to incentivize and improve study retention. A \$20 gift card will be given to the teens after each study assessment (baseline, 6-week, and 12-week) for a total compensation of \$60.
3. Parent Online Survey participants (n=100) will complete an online survey at the baseline, 6-week, and 12-week assessment. Parent inclusion criteria are: (a) parent/guardian of eligible child and (b) able to speak and read English. Parents will be provided a \$10 gift card after each study assessment for a total of \$30.

5A.2. Sources of Research Material. Data from the usability testing will be collected in the form of handwritten notes, audio tapes, computer files, transcriptions and questionnaires. Transcripts of audiotaped discussions will be analyzed via Atlas-ti® content and thematic analysis software to identify consistent and recurrent content and themes in response to discussions. Data gathered from the usability testing will be summarized in notes by research staff to identify usability problems.

Participants (teens and parents) will complete a baseline, a 6-week, and a 12-week assessment during the evaluation period. Data gathered from the questionnaires and surveys will be collected online, using KB's online survey software, QuestionPro®. App usage will be monitored using Web Trends software. All data will be obtained specifically for research purposes. Access to all data will be limited to the Principal Investigator (PI), Co-Investigators, specific project staff, and consultants. Data will be kept confidential and anonymous and will be kept in locked files and secure servers.

5A.3. Potential Risks. There are minimal risks associated with participation in this study. The potential risks in this project are limited to minimal psychological risks. Participation in the usability testing, which requires children to answer general usability questions about the *Pinpoint* tablet app, has slight risks. Participants may be hesitant or uncomfortable responding to questions about their opinions regarding the *Pinpoint* tablet app.

Participation in the evaluation period and the parent online surveys has minimal risks. Participants may be hesitant to answer questions related to (1) knowledge acquisition for communicating about pain and types of SCD pain; (2) the Pain Assessment Tool; (3) SCD general knowledge and self-efficacy, (4) family cohesion, and (5) app usage. All responses collected in this project will not be shared with anyone except project staff. All participants will be allowed to withdraw from the project at any time.

5B. Adequacy of Protection Against Risks

5B.1. Recruitment and Informed Consent. Human Subjects oversight will be conducted by Western Institutional Review Board (WIRB; DHHS IRB Reg. No. 00000533). WIRB will review and approve subject materials (including recruitment materials, consent forms, and survey instruments) and data management procedures prior to study implementation.

Potential study participants will be recruited primarily through nationwide SCD support groups, SCD networks, social media ads, and existing research participant databases. In addition, we have the commitment of the EAB and PAB to assist with recruitment.

For the usability testing, children participants will view the app and provide feedback about its user interface,

ease of use, and perceived barriers. Usability testing sessions will be conducted remotely. In remote usability testing, researchers are in a different location than the users, but both parties are on a web conference call and are sharing screens. Researchers can see what participants are doing, and they can communicate with each other in real time. The researcher provides test participants with activities to complete while using a design or interface, and users typically think out loud as they work on the tasks. The researcher observes the user as they work through the tasks, and ask questions for clarification or to gather more data. The users will complete defined tasks while being observed and complete a usability survey. They will rate their satisfaction with the app with regards to design, appeal, functionality, and navigation using Likert-type scales. Project staff will make notes of issues encountered during testing. Usability testing participants will be asked for assent and parental consent to participate in the usability testing. Consent/assent will be obtained using the procedures below.

For evaluation period, participants will be sent an email describing the study and a link to a screening survey administered on KB's secure server that assesses inclusion criteria and demographic characteristics. The online screener will take about five minutes to complete. If needed, phone recruitment and screening will also be used. After being screened, participants will receive an email to inform them of their eligibility status. Eligible participants will be scheduled for an orientation and baseline assessment, which will be conducted via videoconferencing. Participants will have the study explained and provide online consent (parent) and assent (child). After providing consent and assent, participants will attend a one-on-one orientation. During the orientation, teens will be assisted with app download, provided instructions on how to use the app, and encouraged to use the app daily. Then the baseline assessment session will be conducted via videoconferencing. Participants will complete the (online) baseline survey(s) using their personal smartphone or tablet device, which should take about 30 minutes to complete.

Participants will complete a 6-week assessment of initial changes. An invitation email and text messages containing a link to the survey(s) along with their unique password (PIN number) will be sent. Participants will complete the online survey(s) using either their tablet or smartphone; no videoconferencing will be required for the 6-week assessment.

Participants will complete a 12-week post-test assessment. Participants will meet individually with study staff via videoconference to complete the online survey(s) and a brief post-test interview.

Consenting/Assent procedures are as follows:

A parent will be present and give consent for the child during the videoconference. Children will provide assent. Eligible children will be invited to participate, consented/assented using the following procedures:

1. Research staff will send an introductory email inviting eligible parents and children to participate and follow-up with emails and telephone calls to recruit them.
2. Interested parents will go to the study website to register and complete an online enrollment form, providing contact information (i.e., name, address, telephone numbers [home and mobile phones], and email address[es]) for themselves, their child, and people who can always locate them and their child (i.e., a locator).
3. Each parent and child will sign online consent form/assent form at the study website. If a parent or child does not consent/assent the child will not be enrolled. Participants will give their consent/assent electronically and be able to download and save (or print) a copy of the consent/assent form. The IRB-approved consent/assent forms will describe the purpose of the project, risks and benefits, and selection criteria. Participants will be informed that they have a right to withdraw from the study at any time. No additional data will be collected from participants who decide to withdraw; however, the information collected prior to withdrawal will remain in the study. All correspondence will contain the PIs' email addresses and phone numbers for invited participants to use if they have questions.

Participation in all stages of this Phase II application is entirely voluntary and subjects are free to withdraw from the project at any time without negative consequences. Furthermore, withdrawing from the study will not affect the participants' benefits. No additional data will be collected from participants who decide to withdraw; however, the information collected prior to withdrawal will remain in the study.

5B.2. Protection Against Risk. To minimize potential psychological risk, usability testing facilitators/interviewers will establish ground rules for discussion that includes an open, non-evaluative exchange of

comments and ideas. IRB-approved discussion procedures will be carried out under the supervision of senior project staff. Participants will be told that they do not have to answer any questions that make them uncomfortable and can terminate their participation at any time they wish. Notes, surveys, and data will be accessible only by research personnel. Data forms and computer records will be labeled only with participant identification number. Participant names and study identification numbers will be recorded and stored separately from the research data files.

Any survey questions and discussion transcripts will be de-identified before being submitted for analysis and the Research Assistant will remove any references to individual names or identifier data. There are no clinical data to be captured. Responses to survey questions and participation in discussions will not reasonably place the subjects at risk of criminal or civil liability or be damaging to the subjects' financial standing, employability, or reputation. The data collected on this project will be obtained with the "use of educational tests, survey questions and interview procedures."

To protect privacy and to ensure that the participant is the person completing the app activities, KB will uniquely identify the user's smartphone/tablet based off the device's "hardware footprint". The app will upload all app activity data to the KB secured web server database.

All surveys and data collection forms will be IRB-approved and administered under the supervision of senior project staff. Participants will be told that they do not have to answer any questions which make them uncomfortable and can terminate their participation at any time they wish. Notes, surveys, and data will be accessible only by research personnel. All notes will be stored in locked cabinets; all electronic data files will be stored on KB's secure network servers behind computer firewalls, with routine backup. All identifiers will be stored in secure files and behind computer firewalls and results will be shared in aggregate form only.

The *Pinpoint* app and databases will be hosted on KB's state-of-the-art web server farm. Its Live and Test web servers consist of Windows 2003, Internet Information Server 6.0, dual 2.8 Ghz Processors, 4 Ghz Ram, and 120 Gb Hard Drive space. The SQL Server consists of Windows 2003, Microsoft SQL 2000, 2.8 Ghz Processor, 3 Gb Ram and 240 Gb of hard drive space configured with RAID 5. File sharing and print serving is accomplished through a Windows 2003 dual 3.2 Ghz processor server with 4 Gb RAM and 750 Gb of hard drive space configured with RAID 5. All computers are protected by Norton Corporate Edition Antivirus software. Nightly backup protects against loss of data. Three T1 lines provide Internet access. Usage is monitored with Web Trends to ensure that the server hardware and T1 Internet service is sufficient for the number of hits (and upgraded as necessary). Information stored on KB's web server is protected by a hardware firewall (Cisco PIX); each server has native Windows security software. All the KB servers are connected via 1 Gigabit high speed switched network.

5C. Potential Benefits of the Proposed Research to Participants and Others

The benefits of this research are substantially greater than any risks. Potential benefits for all participants will be the knowledge that one has helped to evaluate a web based application that engages adolescent sickle cell disease patients in precision pain management.

5D. Importance of the Knowledge to be Gained

SCD is the most common inherited blood disorder in the U.S.¹ and affects 70,000 to 100,000 individuals, primarily African Americans and Hispanics.²⁻⁴ SCD causes serious and life-threatening comorbidities such as organ failure, acute chest syndrome, and stroke.^{7,8} Pain is the hallmark symptom.⁹

Pinpoint will be the first app to identify and translate specific pain types for SCD into a gamified app using applied gamification principles while also instructing teens on how to effectively communicate their pain to others. *Pinpoint* also has strong clinical significance. It has the potential to be utilized in tandem with any pediatric care setting and can potentially reduce barriers to obtaining children's self-report by using a medium that they are comfortable with and enjoy, while providing important pain information that affect treatment choices and overall health.

5F. Training in the Ethical Conduct of Research with Human Subjects

The Principal Investigator, Co-Investigators, and all study personnel have completed the required training in the Ethical Conduct of Research with Human Subjects. Necessary documentation will be provided to NIH prior to funds being awarded.

5G. HIPAA Research Authorization

Although we will not be collecting medical information or Protected Health Information, we may email the app content to physicians.

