that is sufficient to detect pre-post changes in primary and secondary outcomes rather than spend resources on securing a sample of which half will not be treated. We will also avoid having parents decline to participate due to the chance their teen will not receive the app. We have included two design aspects to control threats to validity¹⁴⁴: (1) we have a 6-week interim measure to create a time-series on the assessment of change; and (2) we will include a measure of communication and knowledge related to influenza as a nonequivalent dependent variable, which we do not expect will change pre to post as a result of the app despite it being subject to the same history, maturation, or regression threats as our primary and secondary measures. We will also include demographics, especially age of the teen and parental age and education, as covariates in the analysis as statistical controls against threats such as maturation.

A description of the app was provided in **Sections 3C.1d** and **3C.4.3c**. Participants will download the app following the procedures outlined in **Section 3C.7.1**. Project staff will provide users with a one-on-one app orientation and how to use its unique features via videoconferencing. Daily notifications will engage users in daily app use and provide up-to-date information on users' progress. Participant responses will also be used to evaluate additional or on-going support of users' needs. To protect privacy and to ensure that the participant is the person completing the app activities, KB will uniquely identify the user's smartphone/tablet based off the device's "hardware footprint". The app will upload all app activity data to the KB secured web server database.

3C.6. Target Population. There are two populations: teens with SCD and their parent. Inclusion criteria for teens are: (a) age 13-17 years; (b) diagnosed with SCD; (c) own a smartphone or tablet, and (d) read and speak English. Parents will be recruited to complete a parent proxy version of the primary outcome measure (child's knowledge acquisition; see **3C.7.2**), but will not use the app. Parent inclusion criteria are: (a) parent/guardian of eligible child and (b) able to speak and read English.

3C.7. Trial Conduct.

3C.7.1. Recruitment and Visit Procedures.

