Recruitment and Screening: Potential study participants will be recruited through nationwide SCD support groups, SCD networks, social media ads, and existing research participant databases. Recruitment was a challenge during Phase I due to IRB delays at the study hospital. Thus, we reached out to multiple national organizations to assist with Phase I recruitment. During Phase I, a number of organizations expressed interest in being a recruitment center for Phase II. We have four committed organizations and four others have expressed commitment via phone or email communication (see **Letters of Support**). In addition, we have the commitment of the EAB and PAB to assist with recruitment.

Participants will be sent an email describing the study and a link to an eligibility screening survey via KB's secure server. The online screener will take 5 minutes. Phone screening will be used as needed. Participants will receive an email informing them of eligibility. Eligible participants will be scheduled for an orientation/baseline visit which will be conducted via videoconferencing; a reminder email and text message will be sent 3 days prior to the assessment (similar reminders will be sent for 6- and 12-week visits).

Orientation and baseline/pre-test assessment: In a one-on-one orientation session to be conducted via videoconferencing, participants will have the study explained and provide written consent (parent) and assent (child). Immediately following, the teen will complete pre-test surveys online using their personal smartphone or tablet device (see **3C.8**) which should take about 30 minutes to complete. Parents will complete an online survey (proxy measure of the primary outcome). After the surveys, teens will be assisted with app download, provided instructions on how to use the app, and encouraged to use the app daily.

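### Section 5B.1 places app download, instruction and encouragement before the baseline assessment, while 3C.7.1 places the same three steps after it

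*Combined protocol and SAP*

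**What the plan says.** Section 3C.7.1 opens the first contact with an orientation session in which the study is explained and consent and assent are given. The surveys come next: "Immediately following, the teen will complete pre-test surveys online using their personal smartphone or tablet device". The app steps come last: "After the surveys, teens will be assisted with app download", together with instructions and encouragement to use the app.

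Section 5B.1 also begins with consent and assent, followed by a one-on-one orientation. Here the app steps belong to that orientation: "During the orientation, teens will be assisted with app download", with the same instructions and encouragement. The baseline follows: "Then the baseline assessment session will be conducted via videoconferencing".

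Both sections seem to describe a single scheduled contact. In 3C.7.1: "Eligible participants will be scheduled for an orientation/baseline visit which will be conducted via videoconferencing". In 5B.1: "Eligible participants will be scheduled for an orientation and baseline assessment, which will be conducted via videoconferencing". However, 5B.1 gives no interval between orientation and baseline and does not bar app use between the two.

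Two other places bear on the order. Section 3C5.1 says "Participants will download the app following the procedures outlined in" Section 3C.7.1, and it describes the orientation content: "Project staff will provide users with a one-on-one app orientation and how to use its unique features via videoconferencing". Item 2 of 5A.1 mentions both the app orientation and the baseline assessment without ordering them.

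**The concern.** Each teen serves as their own control. Section 3C.5 defines the primary outcome as change in communication knowledge relative to baseline, and 3C5.1 explains why there is no control arm. The baseline is therefore the reference for the whole pre-post comparison.

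Staff who follow 5B.1 as written would take that reference after the teen's first access to the intervention. If some staff follow 5B.1 and others 3C.7.1, baselines would also not be comparable between participants.

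The two safeguards named in 3C5.1 do not repair this. The 6-week measurement is compared with the same baseline. The influenza quiz was chosen because the app should not affect it, so it could not reveal app learning that took place before baseline.

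**Working it through.** No sample size, power or alpha in the SAP depends on the visit order, so there is no figure to reproduce. The check is a comparison of texts.

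**1. The two sequences**

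| Step | 3C.7.1 | 5B.1 |
|---|---|---|
| Study explanation, consent/assent | first | first |
| Baseline surveys | second, directly after consent | third |
| App download, instruction, encouragement | third, after the surveys | second, within the orientation |

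Three steps (download, instruction, encouragement) change sides relative to the baseline. Both sections use explicit sequence words, and both are current text.

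**2. Which order is intended.** Section 3C5.1 points to 3C.7.1 for app download, 3C.7.1 and Figure 7 label the baseline a pre-test, and 3C5.1 states the aim as detecting pre-post change. All of these fit surveys-first. Nothing says that 5B.1 yields to 3C.7.1.

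**3. The word orientation has two senses.** In 3C.7.1 the orientation session starts before the surveys, with the study explanation and consent. Only the app steps follow the surveys. The part of 5B.1 that is out of place is therefore the app part, not the whole session.

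**4. Direction of any bias in knowledge scores.** Let Y0 be the score before any app access, Y12 the 12-week score, and e the amount learned from the app before a late baseline. Assume that the order does not alter Y12.

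- Surveys first: measured gain = Y12 − Y0.
- App first: measured gain = Y12 − (Y0 + e) = (Y12 − Y0) − e.

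If e is positive, the gain is understated by e. If only a fraction p of teens follow the app-first order, the mean gain is understated by p × e. The documents give neither e nor p.

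**5. Is a positive e plausible?** The eight communication areas given as examples of app content in 3C.4.3c are the same eight from which 3C.7.2 draws the communication items of the primary measure (8 of 8). The outcome therefore tests what the app teaches. That does not show that setup help teaches it, since 3C5.1 describes the orientation as covering how to use the app's features.

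**6. The other measures.** Figure 7 schedules 7 measures at baseline, and the order affects when all of them are taken. They are not equally exposed: the influenza quiz is not expected to respond to the app, and 3C.6 says parents do not use it. For self-efficacy, family cohesion and the self-reported domains of the Pain Assessment Tool, the documents support no direction.

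**7. A complication.** The Pain Assessment Tool is one of the 7 baseline measures, but it is also an app module (3C.1d, 3C.4.3c), and 3C.7.2 calls it the app's tool. Sections 3C.8 and 5A.2 say surveys run in online survey software. The documents do not settle how the tool is given at baseline.

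**The case against.** The strongest reply is that 3C.7.1 is the trial-conduct section, 3C5.1 refers app download to it, and 5B.1 is a consent narrative, so staff would follow 3C.7.1 and the conflict is only one of wording. This limits the practical risk, but 5B.1 is a full, current description of the visit in the human-subjects section, with its own explicit order.

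A second reply is that the effect would be slight. On the one-contact reading the exposure is setup help and instructions, and this stands.

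A third is that the Pain Assessment Tool may need the app installed before baseline. If so, 3C.7.1 also needs clarification, and a blanket ban on app content before baseline could not be met. The fix has to allow for this.

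A reader might infer more than the documents support:

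- That the 5B.1 order would produce a false gain. For knowledge scores early learning points the other way, and for the remaining measures no direction is established.
- That teens would use the app for days before baseline. Section 5B.1 states no interval, and both sections read most naturally as one contact.
- That all 7 baseline measures would be distorted. The order governs their timing, but the influenza quiz and the parent proxy are less exposed, as noted above.

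**Conclusion.** The contradiction is certain: 5B.1 and 3C.7.1 put the same three app steps on opposite sides of the baseline, and no other section resolves it. The intended order is clear enough to say that 5B.1 is the text to change.

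The consequence is much less certain. For knowledge scores, a baseline taken after app access would most likely understate the gain. This assumes that any early learning raises the baseline score and that the 12-week score does not depend on the order. The size cannot be estimated from the documents and is probably small if orientation and baseline form one contact. The point deserves correction because the baseline is the pre-post reference in an uncontrolled trial and the correction costs little, not because a material bias has been shown.

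**What to change.** Reorder 5B.1 to match 3C.7.1: study explanation and consent/assent; then the baseline measures for teen and parent; then app download, app instruction and encouragement to use the app. Give item 2 of 5A.1 the same order. The orientation session can still open with the study explanation and consent; only its app steps move.

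Add a sentence that no app module is opened or demonstrated until the baseline measures are complete, with an exception for the Pain Assessment Tool if it is delivered in the app. State whether the baseline Pain Assessment Tool is given through the online survey software or through the app.

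The cost is an edit to two sections, the added statements, and one decision on how the Pain Assessment Tool is delivered. No visits, participants or measures are added.
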